2.4.1 Expected safety profile for BT1718

Haematopoietic changes

Haematological toxicity such as neutropenia, lymphopenia, erythropenia and thrombocytosis are not uncommon in agents that affect the cell cycle and these changes are clinically manageable.

BT1718 is likely to

produce haematological changes in patients and as such, standard haematological evaluations will be undertaken as part of the clinical programme.

Renal and bladder changes

BT1718 and its possible peptidyl metabolites, are expected to be cleared through the kidney and bladder.

Standard blood (serum urea, creatinine) and urine tests (urinalysis for protein and blood) will be undertaken as part of the clinical programme. Further investigations would be initiated as clinically indicated.

Hepatic changes

Hepatotoxicity has been a common finding for the predominantly hepatic-cleared maytansine and antibody-maytansinoid conjugates, but may be minimal for BT1718

However, as a precaution standard liver function tests will be performed as part of the clinical programme. Further investigations or imaging would be initiated as clinically indicated.

Neuronal changes

Peripheral neuropathy is a common side effect of microtubule inhibitors [31] and has been a noted AE experienced with antibody-DM1 conjugates.

. Patients will be evaluated at study

visits for any AEs relating to the nervous system. Symptom-directed clinical examination and further investigations or imaging would be initiated as clinically indicated. Further investigations or imaging would be initiated as clinically indicated

Skin

Patients will be evaluated at study visits for any AEs related to the skin. In addition, DM1 and other chemotherapeutics can cause extravasation and/or are vesicants, irritants, inflammitants or exfoliants⁷ [55, 56] and as a precaution BT1718 will be treated as a vesicant. Patients will be evaluated during treatment and at each study visit for evidence of extravasation. Standard local policies for management of vesicant extravasation will be followed, typically starting with stopping the infusion, aspirating if possible, topical hydrocortisone and ongoing review. The role of specific treatment such as heat or cold packs, dimethyl sulfoxide (DMSO) or hyaluronidase is unknown.

Gastrointestinal changes

⁷ http://www.beatson.scot.nhs.uk/content/mediaassets/doc/Extravasation%20guidance.pdf

Gastrointestinal toxicity is therefore considered unlikely below the MTD in humans. Patients will be evaluated at study visits for any AEs relating to the GI tract (see pancreatic acinar section below). Further investigations or imaging may be initiated if clinically indicated.

Reproductive organ changes

Changes in the reproductive system are a common side effect of agents that affect the cell cycle.

Reproductive changes may be a possible side effect of administration of BT1718. Patients will be advised of the potential impact of BT1718 on fertility and patients will be required to comply with the standard clinical trial contraceptive practices. The Phase I trial will be in refractory/relapsed patients whose prognosis and fertility are likely to be very limited, therefore in this context it is deemed an acceptable risk. Where appropriate for male patients who may be in a position to consider having or extending a family, the possibility of conservation of sperm should be discussed. Patients wishing to do so should also have a discussion of the implications of their own prognosis and of the possible effects of previous therapy on the production, function and genetic health of sperm.

Adrenal changes

Administration of BT1718 could lead to changes in adrenal gland function including the zona glomerulosa (aldosterone secretion). As such, BP and standard clinical chemistry parameters will be evaluated as part of the clinical programme. Persistent unexplained hypo-/hyper-tension or altered potassium levels would be investigated further with serum renin:aldosterone, cortisol or ACTH assays as appropriate, and treatment such as fluids and steroid replacement, or conversely anti-hypertensives, initiated as clinically indicated.

Salivary gland changes

Dry mouth and associated toxicity are a common side effect with chemotherapy [37], with these symptoms tending to resolve within 3 to 4 weeks off treatment.

Patients will be evaluated at study visits for any AEs, including dry mouth. Symptom-directed clinical examination/and or further investigations will be conducted as clinically indicated.

Pancreatic acinar changes

Toxicity might be expected to manifest as impaired exocrine function of the pancreas. Patients will be evaluated at study visits for any AEs relating to the GI tract (see also gastrointestinal section above). Bloating, steatorrhoea and/or diarrhoea may be investigated further with faecal elastase evaluation and treatment such as CREON initiated as clinically indicated.

2.5 Rationale for the proposed trial

By targeting MT1-MMP expressing tumour cells, BT1718 is expected to induce selective tumour cell death. This would be expected to translate into objective radiological responses with an acceptable therapeutic window, and ultimately to improve PFS and OS for patients with MT1-MMP expressing tumours. Preclinical data has demonstrated activity in relevant models and toxicology has indicated monitorable and reversible toxicities, expected to be manageable in the clinic.

BT1718 has low molecular weight (3.5 kDA) in comparison to other conjugated toxin approaches, which enables rapid penetration of tumour tissue. In addition, preclinical PK and toxicokinetics estimates a 15 to 30 minute half-life, which is in contra-distinction to ADCs and suggests a more rapid on-off profile.

Hypothesised advantages over ADCs therefore include reduced systemic exposure of normal tissues to circulating BT1718, the ability to manage toxicity during recovery periods, as well as the improved tumour penetrance. Other potential advantages include a fixed peptide:conjugate ratio of 1:1 (c.f. ADCs where variable conjugation results in mixed populations) and with more scalable manufacturing as a small molecule (c.f. biologics such as ADCs).

Overexpression of MT1-MMP has been reported in NSCLC [3, 4], breast cancer [5, 6, 57] and other solid tumours [7, 8, 9]. Work is ongoing in identifying those tumour types with the highest incidence of MT1-MMP overexpression.

Since the majority of cancers may express some MT1-MMP, and the relationship between efficacy and MT1-MMP expression is not fully delineated the dose escalation phase of the trial will not restrict recruitment based on levels of MT1-MMP expression, and will be open to patients of all solid malignancy types. In the Phase IIa, expansion phase at the optimal dose/schedule(s), patients will be enrolled with tumour types anticipated to commonly overexpress MT1-MMP and where raised high MT1-MMP overexpression is confirmed during prospective screening selection at enrolment. This confirmation of expression will test the hypothesis that MT1-MMP overexpression is expected to translate to favourable clinical outcomes for patients treated with BT1718. The tumour types currently proposed for the Phase IIa are squamous NSCLC, squamous oesophageal cancer and a basket cohort. Other tumour types with a high incidence of MT1-MMP expression may be considered in future expansions cohort(s) and would be specified in a future substantial amendment submitted to MHRA, REC and HRA for approval.

The route of administration will be intravenous as with most peptide-based molecules, as oral dosing would result in degradation.

Initially, twice weekly dosing will be evaluated

During the escalation phase, a once weekly regimen will also be explored, which is expected to be more convenient for patients . The starting dose will

be 0.6 mg/m² twice weekly,

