3.5 Patient evaluability

3.5.1 Response

All patients who meet the eligibility criteria and receive at least one full cycle of IMP or ≥66% of the planned dose exposure of BT1718 within Cycle 1 and 2, and have a baseline assessment of disease and at least one repeat disease assessment will be evaluable for response.

In the expansion cohorts, baseline MT1-MMP H-score must also meet the positivity criteria for the patient to be evaluable.

Repeat assessments after at least four weeks are required in order for a patient to be confirmed as having a complete or partial response (CR or PR). To be assigned a status of stable disease (SD), follow-up measurements must have met the SD criteria at least once and at least six weeks after the initial dose of BT1718 is given.

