4.1.1 Inclusion criteria

- 1. Written (signed and dated) informed consent and be capable of co-operating with treatment and follow-up
- 2. Phase I, dose escalation phase (Stages 1 and 2):
 - Histologically or cytologically proven advanced solid tumour, refractory to conventional treatment, or for which no conventional therapy is considered appropriate by the Investigator or is declined by the patient.

Phase IIa, expansion phase:

- Histologically or cytologically proven advanced solid tumour of particular interest based on pre-clinical and clinical data, refractory to conventional treatment, or for which no conventional therapy is considered appropriate by the Investigator or is declined by the patient. Phase IIa expansion cohorts will be:
 - a. Squamous NSCLC cohort retrospective MT1-MMP testing.
 - b. Basket cohort (advanced solid tumours, excluding patients eligible for one of the other recruiting expansion cohorts) high MT1-MMP expression by IHC assay using archival tumour sample (mandatory fresh tumour samples for those patients without available archival tumour samples or additional analysis is deemed necessary). Retrospective testing may be permitted for tumour types estimated to have high MT1-MMP positivity rates as per the Laboratory manual.
 - c. Additional expansion cohort(s) of squamous oesophageal cancer if confirmed as recruiting by the Sponsor (see Section 3.2).
- At least one measurable lesion according to RECIST Version 1.1, that has had objective progression on or after the last therapy

- 3. Life expectancy of at least 12 weeks
- 4. World Health Organisation (WHO) performance status of 0 1 (Appendix 1)
- 5. Haematological and biochemical indices within the ranges shown below. These measurements should be performed to confirm the patient's eligibility.

Laboratory Test	Value required
Haemoglobin (Hb)	≥90.0 g/L, or ≥100.0 g/L if transfusion within last four weeks
Absolute neutrophil count (ANC)	≥1.5 x 10 ⁹ /L
Platelet count	≥100 x 10 ⁹ /L
Bilirubin	≤1.5 x upper limit of normal (ULN) NB: >1.5 x ULN, acceptable if conjugated bilirubin is ≤1.5 x ULN

Alanine amino-transferase (ALT), aspartate amino-transferase (AST) and alkaline phosphatase (ALP)	≤2.5 x ULN (or ≤5 x ULN if has liver metastases)
Renal function	
Either:	
Serum creatinine	≤1.5 x ULN
Or:	
Calculated creatinine clearance (using the Wright or Cockcroft & Gault [C&G] formula)	GFR ≥50 mL/min (uncorrected value)
Or:	

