5.6.1.2 Phase II, expansion phase

Patients will be replaced in the expansion cohorts if they receive less than one full cycle and less than 66% of the planned dose exposure of BT1718 within Cycle 1 and 2 for reasons other than drug-related (probably or highly probably) toxicity. Patients will also be replaced if retrospective MT1-MMP testing identifies that their baseline tumour sample had a low MTI-MMP H-score.

Replacement of patients will be confirmed by the Sponsor. There may be circumstances based on the emerging data from the trial or BT1718 availability that result in a patient not being replaced. This will be documented by the Sponsor.

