13.5 Pharmacodynamics

13.6 Anti-tumour activity

Documenting anti-tumour activity is a secondary objective of this trial. Patients must receive \geq 66% of the planned dose exposure of BT1718 within Cycle 1 and 2, or at least one full cycle and have a baseline assessment of disease and at least one repeat assessment to be evaluable for response. Patients in the expansion phase must meet the MT1-MMP positivity rate to be evaluable for this objective. Objective responses, the best tumour response achieved by each patient while on trial and the time to progression will be presented in the data listings by cohort.

The response rate (proportion of evaluable patients with objective response) will be reported by cohort. Progression free survival will be calculated from trial entry until the time of documented disease progression or death (whichever occurs first). Patients who are alive and progression free or lost to follow up at the time of analysis will be censored at the time the patient was last known to be alive and progression free. Overall survival will be calculated from trial entry until the time of death from any cause. Patients who are alive or lost to follow up at the time of analysis will be calculated from trial entry until the time of death from any cause. Patients who are alive or lost to follow up at the time of analysis will be censored at the time the patient was last known to be alive. Duration of response will be measured from the date of the first scan where response was seen until date of first RECIST V1.1 progression or death. Median PFS, OS and duration of response will be presented. The PFS and OS rate at 6 months will also be presented. 95% confidence intervals will be reported.

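### The expansion response rate is restricted to MT1-MMP high expressers, partly by exclusion after dosing, so it cannot test whether overexpression drives benefit as Section 2.5 says

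*Protocol*

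**What the plan says.** Section 2.5 explains that Phase IIa will enrol tumour types expected to overexpress MT1-MMP, with overexpression confirmed prospectively at enrolment, and continues: "This confirmation of expression will test the hypothesis that MT1-MMP overexpression is expected to translate to favourable clinical outcomes for patients treated with BT1718". Section 2.1 also describes the confirmation as prospective. For Phase I, Section 2.5 says that "the dose escalation phase of the trial will not restrict recruitment based on levels of MT1-MMP expression".

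The operative sections read differently:

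- **Timing of testing.** The first expansion cohort in Section 4.1.1 is listed as "Squamous NSCLC cohort retrospective MT1-MMP testing". The basket cohort requires "high MT1-MMP expression by IHC assay using archival tumour sample", but retrospective testing may be permitted for tumour types estimated to have high positivity rates. Section 3.2 allows selection by either route.
- **Evaluability.** Section 3.5.1: "In the expansion cohorts, baseline MT1-MMP H-score must also meet the positivity criteria for the patient to be evaluable".
- **Replacement.** Section 5.6.1.2: "Patients will also be replaced if retrospective MT1-MMP testing identifies that their baseline tumour sample had a low MTI-MMP H-score".
- **Analysis.** Section 13.6: "Patients in the expansion phase must meet the MT1-MMP positivity rate to be evaluable for this objective". It adds: "The response rate (proportion of evaluable patients with objective response) will be reported by cohort".

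Section 13.1 judges the response rate in a 16-patient cohort against fixed benchmarks: at least 3 responses for 10% versus 30%, and at least 5 for 20% versus 40%.

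**The concern.** Testing whether overexpression translates into benefit needs outcomes at more than one level of expression. The expansion rules keep only positive patients in the response set, and the rate in that set is compared with fixed benchmarks. A good result would fit equally well with a drug that works because of MT1-MMP and with one that works regardless of it.

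The second issue is when the exclusion happens. Where testing is retrospective, a patient can be dosed, and could be scanned, before the H-score decides whether they count. The trial is open label, and the visible text neither requires the score before the first response scan nor requires it to be read without clinical outcome. A low reading on a known non-responder would remove a failure from the denominator.

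The result has consequences. Under Section 13.1, activity in the squamous NSCLC and basket cohorts is considered in deciding whether to open the oesophageal cohort, and Section 12 lists lack of efficacy among the reasons recruitment may stop.

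**Working it through.** **1. The sections side by side.** Section 2.5 assigns the test to Phase IIa, through confirmation of expression. Sections 3.5.1 and 13.6 admit to the expansion response set only patients meeting the positivity criteria. By rule, the number of low-score patients in that set is 0, so a high-versus-low contrast cannot be estimated from it. On timing, Sections 2.1 and 2.5 (prospective at enrolment) do not agree with Sections 3.2 and 4.1.1 (retrospective testing allowed). Section 5.6.1.2 anticipates that low-score patients will have been dosed.

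**2. The plan's own rule.** Inputs from Section 13.1: n = 16, significance level 0.2, power 80%. With X ~ Binomial(16, p):

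- P(X ≥ 3 | p = 0.10) = 1 − (0.1853 + 0.3294 + 0.2745) = 0.211; P(X ≥ 3 | p = 0.30) = 0.901.
- P(X ≥ 5 | p = 0.20) = 0.202; P(X ≥ 5 | p = 0.40) = 0.833.

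These agree with the stated figures if read as about 0.2 and at least 80%. At true rates of 10, 20, 30 and 40%, the chance of at least 3 responses in 16 is 0.21, 0.65, 0.90 and 0.98. Here p is the response rate in positive patients; the rate in low expressers does not enter.

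**3. Worst case for exclusion after treatment.** Assume 19 patients are dosed, the true response rate is 10% whatever the expression, and three known non-responders are read as low and replaced. All responders stay among the 16 evaluable patients, so the rule is met whenever at least 3 of the 19 respond:

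- P(X ≥ 3 | n = 19, p = 0.10) = 1 − (0.1351 + 0.2852 + 0.2852) = 0.295, against 0.211 for 16.

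If the reading is independent of outcome, the 16 evaluable patients are still 16 draws at 10%, and the probability stays at 0.211.

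**4. How many patients this could touch.** The protocol does not give the share of low scores. Assuming 10 to 30% of about 20 dosed squamous NSCLC patients, 2 to 6 would be affected. Three of 19 (16%) lies within that range.

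**5. What a formal contrast could do.** Assuming response rates of 30% in high and 10% in low expressers, a one-sided Fisher exact test at 0.2 has power 11.5% with 16 high and 4 low, and 39.6% with 16 and 8. Only a descriptive contrast is realistic.

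**The case against.** The strongest reply is that the sentence in Section 2.5 is background, not an objective. The secondary objective in Section 3.1.2 is to look for preliminary signals of efficacy, in the expansion in tumour types with high expression. A positive-only response set fits that. This stands, and it limits the point: the rule suits the objective, but not the property Section 2.5 claims for it.

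A reader might infer that the trial has no contrast in expression at all. The documents do not support that. Phase I was not selected on expression, has retrospective MT1-MMP status where archival tissue was available, and assessed response, although across doses, schedules and tumour types. H-score also varies among positive patients. The tertiary objectives (3.1.3), the research assessments (8.3) and the pharmacodynamics section (13.5) are blanked out, so an exploratory analysis may exist.

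A reader might also infer that low-score patients are lost. They remain evaluable for safety (3.5.2), are followed for progression and survival (7.4.2), and Section 14.6 puts all clinical data in the final listings. They leave the response denominator, not the database.

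Nor does the Sponsor's option in Section 5.6.1.2 not to replace a patient reopen the denominator: Sections 3.5.1 and 13.6 exclude low scores either way. That discretion affects only whether the cohort is topped up.

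Finally, the H-score comes from a baseline sample, and nothing visible says its readers know the outcome; blinding is simply not described. The cut-off may be fixed in the Laboratory manual, and extra tables may be in the statistical analysis plan; neither is at hand. The absence of such tables is therefore not the finding. The finding rests on the exclusion, which the protocol itself fixes, and on what Section 2.5 says the design will do.

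**Conclusion.** The point holds for the expansion response set. Section 2.5 claims a test that Sections 3.5.1 and 13.6 rule out there, and its account of prospective confirmation conflicts with Sections 3.2 and 4.1.1. The expansion response rate measures activity in MT1-MMP-positive tumours and says nothing on whether expression drives it.

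Where testing is retrospective, the rate is also open to bias from exclusions made after treatment. The rise from 0.21 to 0.29 is a worst case that needs all three low readings to fall on known non-responders; it is not an expected effect, and it vanishes if the reading is independent of outcome. The visible text does not secure that independence, but neither does it show that independence was breached.

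**What to change.** 1. In Section 13.6, report response rate, PFS and OS for all dosed patients in each expansion cohort beside the H-score-positive set.
2. Add a descriptive table of response by H-score over all dosed patients, including Phase I patients with a result.
3. State that the H-score is read blind to clinical outcome, against a cut-off fixed beforehand.
4. Reword Section 2.5 to say that the expansion estimates activity in MT1-MMP-positive tumours and that the relation between expression and outcome is exploratory. Reconcile the prospective-at-enrolment wording in Sections 2.1 and 2.5 with Sections 3.2 and 4.1.1.

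The cost is some additional tabulation of data already collected, one sentence on reading, and edits to two background sections. The drawback is that low-score numbers will be small and support description only.

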3 TRIAL DESIGN

3.1 Clinical trial objectives and endpoints

3.1.1 **Primary objectives and endpoints**

Primary objectives	Endpoints
Dose Escalation phase	
To propose a recommended Phase II dose (RP2D) for evaluation by establishing the maximum tolerated dose (MTD) and/or maximum administered dose (MAD), of BT1718 given in patients with advanced solid tumours, at one or more dosing schedules.	Determine a dose at which no more than one out of six patients at the same dose level experiences a probable or highly probable BT1718-related DLT.
Dose escalation and expansion phase	
To assess the safety and toxicity profile of BT1718 in patients with advanced solid tumours.	Determine the frequency and causality of each AE to BT1718 and grade severity according to NCI CTCAE Version 4.02.
	The causality of all AEs will be assessed by the Investigator.

3.1.2 Secondary objectives and endpoints

Secondary objectives	Endpoints
Dose escalation phase and expansion phase	
To investigate the pharmacokinetic (PK) behaviour of BT1718 in human	Measurement of C_{max} , AUC, terminal elimination half-life ($t_{1/2}$), and other PK parameters of BT1718 in plasma, both as an intact and cleaved molecule.
Dose escalation and expansion phase	
To assess preliminary signals of BT1718 efficacy in dose escalation and in relevant tumour types with high expression of membrane type 1 matrix	Assess anti-tumour response according to Response Evaluation Criteria in Solid Tumours (RECIST) Version 1.1.
metalloproteinase (MT1-MMP) in the expansion phase	Estimate progression-free survival, progression-free survival rate at six months, and OS (where available). Estimate duration of response.

3.1.3 Tertiary objectives and endpoints

3.2 Design of the clinical trial

This is a multi-centre, FIH, Phase I/IIa, open label dose escalation trial with an expansion phase, in patients with advanced solid tumours.

This clinical trial will consist of two phases, Phase I and Phase IIa (Figure 3).

Phase I, dose escalation phase:

Phase I will consist of Stage 1 and Stage 2. Stage 2 may commence before Stage 1 is completed:

• **Stage 1** - BT1718 will be administered intravenously **twice weekly** for three out of four weeks until the RP2D and/or MTD is established.

Stage 1 will start with single patient cohorts and dose increases will initially be up to a maximum of 100%, driven by reported safety and any available PK data until such time that a Grade 2 or greater AE considered to be at least probably related to BT1718 is observed or until the dose exceeds 6 mg/m² twice weekly (i.e. 12 mg/m² over the week). Subsequent cohorts will revert to a standard 3+3 format with dose escalation steps up to 100% driven by reported safety and available PK data.

• **Stage 2** - BT1718 will be administered intravenously **once weekly** for three out of four weeks until the RP2D and/or MTD is established.

Stage 2 will open at a dose where there is expectation of potential biological activity based on available toxicity, PK and/or PD data from Stage 1. This stage will follow a 3+3 dose escalation design and will include a minimum of three evaluable patients at each dose level. Dose increases will be up to 100%, driven by reported safety and available PK data.

Phase I of the trial has completed.

Phase IIa, expansion phase

Phase IIa will consist of two or more expansion cohorts to include tumour types known to commonly over-express MT1-MMP and where MT1-MMP overexpression is confirmed during retrospective or prospective selection.

- Squamous NSCLC cohort- BT1718 will be administered intravenously at the once weekly RP2D established in Phase I, Stage 2 and will include approximately 16 patients, with MT1-MMP positive squamous NSCLC (see section 5.4.4 for further details on RP2D dose adjustments). It is expected that a minimum of eight patients will have pre and post treatment biopsies (see section 7.1.3 and 7.2.2 for further details).
- **Basket cohort-** BT1718 will be administered intravenously at the **once weekly** RP2D established in Phase I, Stage 2 in approximately 16 patients with advanced solid tumours (excluding patients eligible for one of the other recruiting expansion cohorts). See section 5.4.4 for further details on RP2D dose adjustments It is expected that all patients (except patients with a very high MT1-MMP H-score if agreed with the Sponsor and PI) will have pre and post treatment biopsies (see sections 7.1.3 and 7.2.2 for further details). The squamous NSCLC and basket cohorts will run in parallel.
- Additional expansion cohort(s) an additional expansion cohort of approximately 16 evaluable patients with squamous oesophageal cancer may be opened after review of data obtained from the squamous NSCLC and basket expansion cohorts by the Joint Development
Committee comprising of team members from the Sponsor, Bicycle Therapeutics Ltd and Chief Investigator (CI). It is expected that a minimum of eight patients will have pre and post treatment biopsies (see section 7.1.3 and 7.2.2 for further details). Other tumour types with a high incidence of MT1-MMP expression may be considered in future expansion cohort(s) and would be specified in a future amendment.

In Phase I, Stages 1 and 2, it is expected between 50 to 60 patients with advanced solid tumours, whose tumours have progressed through any suitable standard therapies, will be entered into this study. The final number of patients will depend on the number of dose escalations required to identify the MTD and/or RP2D, at one or more dosing schedules. In Phase IIa it is expected that up to an additional 70 patients will be evaluated.

In Phase I, Stage 1, BT1718 will be administered intravenously **twice weekly** for three out of four weeks (dosing on Days 1, 4, 8, 11, 15 and 18). The starting dose will be 0.6 mg/m² and each cycle will last 28 days. Patients may continue treatment until disease progression (depending on the availability of BT1718).

In Phase I, Stage 2, BT1718 will be administered intravenously **once weekly** for three out of four weeks (dosing on Days 1, 8 and 15). The starting dose of the once weekly regime will be up to 100% of the overall weekly dose from the last completed cohort deemed safe from the twice weekly schedule (Phase I, Stage 1). Patients may continue treatment until disease progression (depending on the availability of BT1718).

Alternative dosing schedules may be considered by the Sponsor based on emerging data during the study, for example if the toxicology profile is benign with the twice weekly dosing regimen, continuous twice weekly dosing may be evaluated. Emerging data obtained during Phase I will be used in the decision to proceed with the Phase IIa stages. In addition, depending on the patient populations selected, an increased dosing frequency may also be considered. If any changes are made to the dosing schedule a substantial amendment will be submitted to the MHRA, REC and HRA for approval.

Phase I of the trial has completed.

Figure 3 Study design schema

Page 37 of 99

